6 STUDY TREATMENTS AND ADMINISTRATION

6.1 IMCnyeso Study Treatment

IMCnyeso will be supplied by the Sponsor, Immunocore.

Dose and treatment schedules are described in [Table 6-1](#) below.

Table 6-1: Dose and Treatment Schedule

Study Treatments	Pharmaceutical Form and Route of Administration	Dose	Frequency and/or Regimen
IMCnyeso	Liquid in vial for intravenous infusion (single-use vials)	Dose determined by cohort level	Every week

IMCnyeso will be supplied as a sterile, frozen solution, in individual, single-use glass vials at a concentration of 0.5 mg/mL. Each vial is to be used for 1 dose / 1 patient.

The drug solution contains citrate (5.2 mM), phosphate (14.8 mM), trehalose 5% (weight/volume), mannitol 1% (weight/volume), and Tween-20 0.05% (weight/volume). The frozen solution appears clear, colorless, or pale yellow when thawed and has a pH 6.0.

6.2 Treatment Regimen and In-Patient Hospitalization

Patients enrolled in this study will receive treatment with single-agent IMCnyeso dosed weekly on Days 1, 8, 15, and 22 of each 4-week cycle. All dosages prescribed and dispensed to patients and all dose changes during the study must be recorded on the Dosage Administration Record and electronic case report form (eCRF).

For each administration of study medication, a physician must be present at the site or immediately available to respond to emergencies. Study sites will be instructed on the conservative management of symptoms associated with CRS (eg, hypotension), as described in [Section 6.15](#). Fully functional resuscitation equipment and medications to handle acute infusion-related emergencies (eg, anaphylaxis, CRS) must be available at each study site.

Patients will be hospitalized for 2 nights following the administration of the first dose (C1D1) of IMCnyeso and will remain at the site for overnight observation following administration of the second dose (C1D8). In addition, patients receiving intra-patient escalation (IPE) will be hospitalized overnight following the first three doses (C1D1, C1D8, and C1D15). After reviewing safety, PK, and cytokine data from at least 3 patients enrolled at a given dose level, the SST may decide that 1 night of hospitalization is adequate after the first dose for subsequent

patients (with longer hospitalization if indicated). After Phase I is completed and the SST has reviewed all available relevant data for at least 6 patients at the RP2D, the SST may decide to reduce the minimum required monitoring time during the Phase II portion of the study to no less than 8 hours post-end of infusion on C1D1, C1D8, and/or C1D15 (with longer hospitalization if clinically indicated). Patients who experience certain AEs may require additional in-patient monitoring as described in [Section 6.15](#).

6.3 IMCnyeso Handling, Storage, and Preparation

IMCnyeso vials must be stored frozen below -60°C until ready for use.

When required, 1 vial per dose / 1 vial per patient should be thawed at room temperature or at 2°C–8°C. The pharmacy preparation involves the dilution of IMCnyeso using 50 mL or 100 mL 0.9% (weight/volume) sodium chloride infusion bags to which human serum albumin (HSA) has been added at a specified concentration. Due to the low IMCnyeso doses administered in this study, the dilution for administration may require the use of more than 1 infusion bag. Detailed instructions for preparation of doses and provision of dilution bags and HSA will be provided in the Pharmacy Handling Instruction document.

The start time for the expiry calculation is the time the container closure integrity is breached. The prepared IV bag containing IMCnyeso may be stored at room temperature for up to 4 hours or at 2°C–8°C for up to 24 hours. If refrigerated, 30 minutes should be allowed for equilibration to room temperature and total room temperature exposure, including equilibration and infusion must not exceed 4 hours.

6.4 Study Drug Administration

For each patient, the first dose will be infused over 2 hours (± 15 minutes); for dose levels ≤ 30 mcg; the first dose may be infused over 1 hour (± 10 minutes). If the first dose is well tolerated without \geq Grade 2 infusion and/or a hypersensitivity reaction, a given patient's subsequent infusion times may be reduced to 1 hour (± 10 minutes) starting at C1D8, and further reduced to 30 minutes (± 10 minutes) starting at C3D1 provided the above conditions continue to be met. Investigators may prolong the infusion time for individual patients if medically indicated at any time.

The entire contents of the IV bag will be administered using an infusion pump. A further 30 mL of 0.9% sodium chloride should be used to flush the line after the IMCnyeso solution has been infused. The infusion rate should not be changed, unless necessary to manage acute reactions. If the line is not flushed, this must be documented.

The initial dosing of patients in the dose-escalation cohorts will be staggered, with at least a 1-week interval between the first 2 patients at each dose level. The IRS will be used to control

patient allocation to treatment and ensure the dosing intervals and cohort recruitment complies with the protocol.

Please refer to [Section 6.12](#) for guidance regarding pre-medication and interruption of anti-hypertensive medications around the time of each dose.

6.5 Study Drug Compliance and Accountability

Study treatment will be administered to the patient at the study site by trained study staff.

Patient compliance with the prescribed regimen will be assured as all administrations will be performed by site staff under the supervision of the Study Investigator or his/her designee.

The Investigator or his/her designee must maintain accurate records of the receipt and dispensing of all study treatment according to local institutional drug accountability processes. Drug accountability documentation will be reviewed by the Study Medical Monitor during site visits and at the completion of the study.

6.6 Drug Supply, Storage, and Disposal

Study supplies must be received by designated personnel at the study site, handled and stored safely and kept in a secured location where only the Investigator and designated Site personnel have access.

Upon receipt, IMCnyeso vials should be recorded on the Drug Accountability documents and placed in a freezer below -60°C, as specified on the drug label. The freezer used for storage should be monitored, alarmed and the Sponsor informed of any temperature excursions. In the event of a temperature excursion any affected supplies should be quarantined, and the Sponsor contacted immediately.

All IMCnyeso supplies remaining at the end of the study (following appropriate drug accountability procedures) will be destroyed following approval from the Sponsor. This destruction will be performed per local institutional practice at the study site or at a third-party vendor, as appropriate. All destruction of study medications must be documented appropriately.

6.7 Patient Numbering and Treatment Assignment

Patients are identified in the study by a 5-digit number that is assigned by the IRS at the time the patient is first consented for the study. The 5-digits are made up of a 2-digit site identifier followed by a 3-digit sequential patient number suffix. This number is retained throughout the patient's participation in the study and ensures that each patient is numbered uniquely across the entire study database.

6.8 Dose-limiting Toxicities Observation Period

The DLT observation period is defined in [Section 6.10.2](#)

6.9 Starting Dose Rationale

The rationale for the QW dosing regimen in this study are based on the proof-of-concept clinical study of tebentafusp where manageable toxicity was observed with QW dosing of tebentafusp, as well as single-agent anti-tumor activity in both uveal and cutaneous melanoma.

IMCnyeso is a highly human-specific fusion protein. Neither the anti-CD3 nor the TCR portions cross react with any of the standard toxicology species, as discussed in [Section 1.3](#). Therefore, there is no relevant toxicology species to enable the setting of a starting dose using the conventional no adverse effect level (NOAEL) method. In the absence of a relevant toxicology species, MABEL, with receptor occupancy calculations, was used to set a safe starting dose. Derivation of the first clinical dose using the MABEL is shown below.

In vitro pharmacology assays measuring the efficacy of IMCnyeso against cancer cell lines were used to define the MABEL. In these assays, human T cells were added to target cells with different concentrations of IMCnyeso to determine the effects of cytokine release and killing induced at the given concentrations of IMCnyeso. The target cells used were HLA-A*02:01 positive and NY-ESO-1 positive cancer cells, which in the presence of IMCnyeso, induce the CD3 positive effector T cells in the PBMC population to both release IFN- γ and kill the tumor cells. In general, IFN- γ release is observed at IMCnyeso concentrations that are lower than the concentrations required for the observation of target-cell killing. Based on the killing assays and IFN- γ release assays, the MABEL observed in the in vitro assays for IMCnyeso is 5 pM.

The acceptable starting dose in the Phase I dose-escalation study is defined as the IV dose of IMCnyeso with a predicted C_{max} of serum at the MABEL (5 pM) and a receptor occupancy between 10%–30% at C_{max} . The use of C_{max} as the PK determinant of the starting dose prediction is based on the observed toxicity profile of the first ImmTAC in the clinic, tebentafusp, where it was observed that the related and more severe toxicities are observed in the immediate hours following dosing, when the concentration of tebentafusp was maximal. These data suggest that toxicity is related to the maximal plasma concentration more than the overall exposure or the area under the curve (AUC).

Thus, the determination of the starting dose is as follows:

- Given the observation of immediate rash and hypotension following administration of tebentafusp in patients, the appropriate volume of distribution (V_D) of an ImmTAC would incorporate both the blood and tissue compartments. A total V_D of 8 L was

assumed for IMCnyeso based on the observed volume of distribution of tebentafusp in patients

- The molecular weight of the IMCnyeso is 77 kDa; therefore, the expected concentration of IMCnyeso in the serum where a minimal biological effect (ie, < 5 pM) would occur is approximately 400 pg/mL
- The PK data in C57BL/6 mice indicates that IMCnyeso displays linear kinetics upon IV bolus injection with a $t_{1/2}$ of 2–3 hours, in accordance with that observed for tebentafusp
- Assuming a V_D of 8 L and an 80-kg patient, the absolute dose to achieve a C_{max} of 400 pg/mL is 3 mcg
- With the K_D (equilibrium dissociation constant) of 41 pM, the receptor occupancy (Saber, 2016) is anticipated to be approximately 10%

6.10 Dose-Escalation Decision Making

Dosing will begin with the first cohort at the starting dose of 3 mcg QW (Table 6-2). All doses administered to subsequent cohorts of patients will be determined by the SST and will be guided by the BLRM and will be subject to both the EWOC principle and the escalation rule.

Dose-escalation decisions will be made by the SST, which will consist of the Study Investigators, the Sponsor Medical Monitor, and a statistician. For each cohort, dose escalation or de-escalation decisions will be based on the SST's review of all relevant data available, from all dose levels evaluated in the ongoing study, including safety information, DLTs, all \geq Grade 2 toxicity data, PK, and pharmacodynamic data from evaluable patients (as defined in Section 6.10.2). The data and BLRM dose recommendations will be discussed and agreed upon during the dose-escalation teleconference (DETC), and all decisions will be documented in the meeting minutes and shared with all participating Principal Investigators.

If toxicity resolves following appropriate management and provided treatment discontinuation criteria are not met (see Section 6.16), patients experiencing DLTs may continue treatment with IMCnyeso only after agreement with the Sponsor Medical Monitor. With each dose cohort in Phase I, determination of the next dose to be tested in the dose escalation will be guided by the BLRM. Decision making will be based on all evaluable patients in the dose-determining set (DDS) at each cohort level (see Section 6.10.1). At each decision point, the BLRM provides an estimate of all dose levels of IMCnyeso that do not exceed the MTD and incorporates all DLT information at all dose levels for this estimation (see Section 9). In general, the next dose will have the highest chance that the true DLT rate will fall in the target interval (16%–33%) and will always satisfy the EWOC principle. In all cases, the dose for the next cohort will not exceed a 3.34-fold increase from the previous dose. Smaller dose increases may be recommended by the

Investigators and Sponsor upon consideration of all available clinical data. Further details of the BLRM including additional simulated escalation pathways are provided in [Section 13.3](#).

The estimated dose levels to be tested in this study (in the scenario that no DLT are reported) are shown in [Table 6-2](#). Actual doses will be determined using the BLRM and must be agreed upon by the SST.

Table 6-2: Example IMCnyeso Dose Levels for Phase I Dose Escalation

Dose Level	Estimated IMCnyeso Dose Level	Planned Enrollment
1 (starting dose)	3 mcg	2–6
2	10 mcg	2–6
3	30 mcg	3–6
4	100 mcg	3–6
5	190 mcg	3–6

To better understand the safety, tolerability, and PK profile of single-agent IMCnyeso, additional cohorts of patients may be enrolled at preceding dose levels or intermediate dose levels, before or in parallel, while proceeding with further dose escalation. The outcome from these cohorts will be included in the BLRM.

If the first 2 patients in a previously untested dose level experience a DLT, additional enrollment in that cohort will stop, the BLRM will be updated with this new information, and the SST will evaluate the available safety, PK, and pharmacodynamic data. By incorporating information gained at the preceding dose levels and provided the BLRM predicts that the risk of excessive toxicity remains below 25% (EWOC), additional patients may be enrolled at this dose level or a lower dose level as agreed upon by the SST.

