Study Design	
Phase I Dose Escalation:
 
Dosing will begin with the minimum anticipated biological effect level (MABEL) dose as determined by in vitro toxicology studies. Cohorts will initially enroll 3 to 6 patients. If necessary and deemed appropriate by the Study Safety Team (SST), additional patients may be enrolled in a given cohort to make informed dosing decisions. Cohorts of 2 patients may be considered for the first 2 doses. The initial dosing of patients in Phase I will be staggered, with at least a 1-week interval between the first 2 patients treated at each dose level.
 
Patients will be observed for dose-limiting toxicities (DLTs) for a period of 1 cycle (28 days). Dose-escalation or de-escalation decisions will be determined following review of all available safety, PK, and efficacy data, and the dosing recommendations will be primarily guided by the Bayesian Logistic Regression Model (BLRM). The key decisions of dose escalation or de-escalation and identification of the MTD and/or the RP2D will be made by the SST and will occur during the dose-escalation teleconferences (DETC), which will be held once all patients in a given dosing cohort have completed DLT evaluation. All dosing decisions will be agreed upon and documented in the DETC meeting minutes. The SST will include the Study Investigators, the Sponsor Medical Monitor, and a statistician.
 
If the emerging safety profile indicates that the severity of cytokine-mediated AEs tends to become less severe following repeated dosing, the SST may initiate a 1-step or 2-step intra-patient escalation (IPE) regimen and/or allow pre-medication as these approaches have been beneficial for related therapeutics.
 
Approximately 27 patients are predicted to be enrolled in Phase I.
 
Phase II Expansion:
 
Following the identification of the MTD and/or RP2D in Phase I, patients may be enrolled into the 3 Phase II expansion cohorts (NSCLC, urothelial carcinoma, and synovial sarcoma) to make a preliminary assessment of the anti-tumor activity of single-agent IMCnyeso at the RP2D in these disease settings.
 
A Simon two-stage design will be used for each Phase II cohort. If there are no responses among the first 9 patients in a cohort, then accrual in that cohort will stop. If there is at least one response, at the discretion of the Sponsor up to an additional 15 patients may be accrued for a total of up to 24 patients (with at least 3 responses to support further evaluation).

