3.1 Phase I Dose Escalation

Phase I dose escalation will enroll patients with advanced NSCLC, melanoma, urothelial carcinoma, or synovial sarcoma. The primary objective is to determine the MTD and/or RP2D of IMCnyeso as a monotherapy in these patients.

Cohorts will initially enroll 3–6 patients. If necessary and deemed appropriate by the SST, additional patients may be enrolled in a given cohort to make informed dosing decisions. Cohorts of 2 patients may be considered for the first 2 doses. If any ≥ Grade 2 toxicities suspected related to IMCnyeso are observed during the first 2 cohorts, the cohorts should then be expanded following a discussion among the SST. Dosing will start with 3 mcg, which is the MABEL, as determined by in vitro toxicology studies (see [Section 6.9](#)). Phase I is estimated to enroll approximately 27 patients (see [Section 9.9.1](#)).

The initial dosing of patients in dose-escalation will be staggered, with at least a 1-week interval between the first 2 patients treated at each dose level. The integrated response system (IRS) will be used to control patient allocation to treatment and ensure the dosing intervals and cohort recruitment complies with the protocol.

The key decisions of dose escalation or de-escalation and identification of the MTD and/or the RP2D will be made by the SST and guided by the BLRM, as discussed in [Section 6.10](#).

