9.7 Exploratory Analyses

9.8 Interim Analysis

No formal interim analysis is planned during Phase I. The BLRM will be updated after each dose-escalation cohort and the MTD / RP2D will be determined at the end of Phase I (Section 6.10).

A formal interim analysis will be conducted during Phase II. ORR will be evaluated for the first 9 patients in each Phase II cohort to determine whether enrollment may continue (Section 9.9.2).

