13.3.3 Sample Paths

The tables in this section ([Table 13-9](#), [Table 13-10](#), [Table 13-11](#), and [Table 13-12](#)) illustrate various possible paths of dose recommendation and state of the N-CRM model given various response patterns that might be observed in the study.

Table 13-9: Scenario 1, No DLT Reported at Any Dose

Dose (mcg)	Number of DLTs / Number of Patients Treated	Estimated MTD	Recommended Next Dose
3	0 / 3	38	10
10	0 / 3	67	30
30	0 / 3	185	100
100	0 / 3	198	195
195	0 / 3	>200	200

DLT = dose-limiting toxicity; MTD = maximum tolerated dose.

Table 13-10: Scenario 2, One DLT Reported at 30 mcg Dose

Dose (mcg)	Number of DLTs / Number of Patients Treated	Estimated MTD	Recommended Next Dose
3	0 / 3	38	10
10	0 / 3	67	30
30	1 / 3	185	100
25	0 / 3	35	35
35	0 / 3	77	75
75	0 / 3	148	145
145	0 / 3	>200	200
200	0 / 3	>200	200
200	0 / 3	>200	Stop

DLT = dose-limiting toxicity; MTD = maximum tolerated dose.

Table 13-11: Scenario 3, Two DLTs Reported at 100 mcg Dose

Dose	Number of DLTs / Number of Patients Treated	Estimated MTD	Recommended Next Dose
3	0 / 3	38	10
10	0 / 3	67	30
30	0 / 3	185	100
100	2 / 3	61	60
60	0 / 3	70	70
70	0 / 3	78	75
75	0 / 3	87	85
85	0 / 3	100	100
100	2 / 3	83	80
80	0 / 3	87	85
85	0 / 3	91	90
90	0 / 3	97	Stop

DLT = dose-limiting toxicity; MTD = maximum tolerated dose.

Table 13-12: Scenario 4, One DLT at 30 mcg, 2 DLTs at 145 mcg and 2 DLTs at 100 mcg Dose

Dose	Number of DLTs / Number of Patients Treated	Estimated MTD	Recommended Next Dose
3	0 / 3	38	10
10	0 / 3	67	30
30	0 / 3	28	25
25	1 / 3	35	35
35	0 / 3	77	75
75	0 / 3	148	145
145	2 / 3	87	85
85	0 / 3	99	95
95	0 / 3	109	105
105	2 / 3	93	90
90	0 / 3	99	Stop

DLT = dose-limiting toxicity; MTD = maximum tolerated dose.

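### In Phase I cohorts larger than 3, the only written within-cohort stop depends on the order of the DLTs, so a second DLT on patient 3 or 4 requires no overdose check before the remaining places are filled

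*Protocol*

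**What the plan says.** Protocol 6.10 states the rule: "If the first 2 patients in a previously untested dose level experience a DLT, additional enrollment in that cohort will stop". The model is then updated, the Study Safety Team (SST) reviews the data, and "provided the BLRM predicts that the risk of excessive toxicity remains below 25% (EWOC), additional patients may be enrolled at this dose level" or at a lower one. SAP 3.4 repeats this.

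The surrounding text sets the conditions in which the rule operates:

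- **Cohort size.** Protocol 3.1 and Table 6-2 give 3 to 6 patients (2 is possible at the first two doses). If the SST sees a need, "additional patients may be enrolled in a given cohort to make informed dosing decisions". SAP Table 1 lists cohorts of 4, 3, 5, 3, 5 and 4, and a seventh planned at 6.
- **Stagger.** Dosing is staggered "with at least a 1-week interval between the first 2 patients treated at each dose level". No interval is set from patient 3 onward. The DLT window is 28 days.
- **Model update.** Protocol 9.8: "The BLRM will be updated after each dose-escalation cohort". Section 13.3.1 says the same.
- **Decision meeting.** The Synopsis describes a dose-escalation teleconference "which will be held once all patients in a given dosing cohort have completed DLT evaluation".
- **Overdose control.** Protocol 6.10 says the next dose "will always satisfy the EWOC principle", and the Synopsis also ties the 25% limit to the next cohort. Section 2.1 describes the method as controlling DLT risk in future patients on the study.
- **Notification.** Protocol 8.5 requires DLTs to reach the sponsor within 24 hours. No text links that notice to a pause or a model update.

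**The concern.** The protocol already accepts that two DLTs early in a new cohort call for a model check before anyone else receives that dose. It requires the check only when those DLTs fall on patients 1 and 2. DLTs in patients 1 and 3, or 2 and 3, carry nearly the same information, yet require nothing until the cohort is complete. The restriction to a previously untested dose adds a second gap: Table 13-11 returns to 100 mcg after lower doses and again records 2/3, and there the rule could not fire even for the first two patients.

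At stake are the patients who fill the remaining places of a cohort of 4 to 6. They may start at a dose that the protocol's own model would decline for a new cohort.

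**Working it through.** **Step 1: the plan's own figure.** Table 13-11 ("Scenario 3, Two DLTs Reported at 100 mcg Dose") prints a recommended next dose of 60 mcg after 0/3 at 3, 10 and 30 mcg and 2/3 at 100 mcg.

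Model (Protocol 13.3.1): logit p(d) = α + β·d, with α and γ = ln β normal. Table 13-6 gives means −2.95 and −5, 2.75 for each spread parameter, and correlation 0. Table 13-7 adds six pseudo-patients. A dose is eligible if it is at most 3.34 times the highest dose with at least 3 known outcomes and P(p(d) ≥ 0.33) < 0.25. The recommendation is the eligible dose with the largest P(0.16 ≤ p(d) < 0.33). I integrated the posterior on a grid.

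The printed inputs do not reproduce Table 13-8, so I carried several readings of the prior.

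**Step 2: the probability of excessive toxicity at 100 mcg**, after 0/3 at each lower dose (limit 0.25):

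| Reading of the prior | Largest gap to Table 13-8 | Next dose after 2/3 | 2/3 | 2/4 | 2/5 | 2/6 |
|---|---|---|---|---|---|---|
| 2.75 as SD, six pseudo-patients (as printed) | 0.22 | 80 | 0.36 | 0.28 | 0.22 | 0.16 |
| 2.75 as variance, six pseudo-patients | 0.22 | 80 | 0.36 | 0.28 | 0.22 | 0.16 |
| 2.75 as SD, no pseudo-patients | 0.22 | 60 to 65, by grid | 0.69 | 0.49 | 0.35 | 0.245 |
| 2.75 as variance, no pseudo-patients | 0.04 | 60 | 0.63 | 0.44 | 0.31 | 0.22 |
| Prior fitted to Table 13-8 | not exact | 60 | 0.59 | 0.41 | 0.29 | 0.20 |

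Every reading rejects 100 mcg after 2/3 and after 2/4. A 6-patient cohort then has 3 or 2 places left. A 5-patient cohort has 2 or 1. A 4-patient cohort has 1 after 2/3 and none after 2/4. After 2/5 the answer depends on the reading, and after 2/6 no reading rejects the dose.

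**Step 3: other doses.** At 145 mcg, following the path in the title of Table 13-12 (one DLT at 30 mcg), the four readings other than the fitted prior give 0.57 to 0.60 after 2/3 and 0.43 to 0.46 after 2/4. They recommend 90 or 95 mcg against the printed 85, so this path is matched only approximately. At 30 mcg the result turns on the prior. With six pseudo-patients no count of two DLTs exceeds 0.16. The two readings closest to Table 13-8 give 0.41 to 0.44 after 2/3 and 0.18 to 0.20 after 2/5.

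**Step 4: how often the order matters.** Let p be the true DLT rate, q = 1 − p, with independent outcomes.

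- Written rule fires: p² = 0.09 / 0.16 / 0.25 for p = 0.30 / 0.40 / 0.50.
- Second DLT on patient 3: 2p²q = 0.126 / 0.192 / 0.250.
- Second DLT on patient 4: 3p²q² = 0.132 / 0.173 / 0.188.
- Patient 3 or 4: 0.258 / 0.365 / 0.438.

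These apply to cohorts that reach at least 4 patients.

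**The case against.** - **Scope of EWOC.** A reader might infer that the protocol contradicts itself by allowing enrolment at a dose that fails EWOC. The documents do not support that. The limit is worded for the next cohort's dose, and no text requires a cohort to be filled to 6. This is a design gap, not a breach of a stated rule.
- **Cohorts of 3.** Every printed sample path uses cohorts of 3. Such a cohort is full at 2/3 and goes straight to the model. The gap needs a larger or enlarged cohort. That is realistic: five of the seven rows in SAP Table 1 exceed 3, although some of those patients may be replacements for non-evaluable ones.
- **What Table 13-11 shows.** It prints an estimated MTD and a recommended dose, not the EWOC probability. A lower recommendation can also come from maximising target-band probability. Ineligibility of 100 mcg rests on the recomputation above.
- **Any two DLTs.** It is tempting to say that two DLTs in any order make the model reject the dose. At 100 mcg the 2/5 and 2/6 results do not support this, nor do the pseudo-patient readings at 30 mcg.
- **The 30-100-300 mcg cohort.** It is planned at 6 under the same rule, but these posteriors do not carry over. Protocol 13.3.1 calls for a separate model for target doses above 150 mcg following intra-patient escalation, and section 6.10.1 attributes each DLT to the most recent dose.
- **SST judgement and timing.** The SST can pause enrolment at its discretion, but nothing requires it to. Later patients may also have been dosed before the second DLT appears, which reduces the number a pause would spare.

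These points narrow the finding. None explains why DLT order should decide whether the check is made.

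**Conclusion.** The point holds for cohorts larger than 3 when the second DLT falls on patient 3 or 4 while places remain. At 100 mcg after clean lower doses, the probability of excessive toxicity is then 0.36 to 0.69 (2/3) or 0.28 to 0.49 (2/4) against a limit of 0.25. The readings that land on or near the printed 60 mcg give the upper part of each range. For true DLT rates of 30 to 50%, the second DLT lands on patient 3 or 4 more often than the written rule fires.

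The size rests on the reading of the prior, on independent outcomes, and on counting DLT-free patients as evaluable. If a DLT-free patient is still inside the 28-day window and is left out, the data become 2/2 and the probability rises to 0.46 to 0.93. No reading reproduces Table 13-8 exactly, so the ranges should be quoted rather than any single value. The calculation tests the design rule and does not describe events in the trial: Protocol 1.4 reports no DLT as of 22 January 2020.

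**What to change.** Reconcile Protocol 6.10 and SAP 3.4 with the Synopsis (timing of the teleconference, scope of EWOC), section 2.1 and section 13.3.1 on what happens when a second DLT occurs after patient 2. The existing consequence is to pause the cohort, update the model, hold SST review, and resume at that dose only if EWOC is met. It should not depend on DLT order or on the dose being previously untested.

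Two details need wording:

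- Tie resumption to the model's EWOC result, not to a fixed DLT count. Cohorts may be enlarged, and a bare count of two would also halt a cohort at 2/12 = 17%, inside the 16% to 33% target band.
- State how patients still inside the 28-day window enter a mid-cohort update. Under section 6.10.2, a DLT-free patient counts only after at least 28 days of observation.

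The cost is a short enrolment pause, an extra model run and matching text in both documents. Where the model accepts the dose, enrolment resumes.
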